11.1.1.2. Serious Adverse Event

An SAE is an AE/reaction that results in any of the following outcomes:

- Death
- Is life-threatening (subject is at immediate risk of death at the time of the event; it does not refer to an event that hypothetically might have caused death if it were more severe)
- Requires subject hospitalization (formal admission to a hospital for medical reasons) or prolongation of existing hospitalization (see below for details on hospitalization SAE criteria)
- Results in persistent or significant disability/incapacity (ie, there is a substantial disruption of a person's ability to carry out normal life functions)
- Is a congenital anomaly/birth defect

- Important medical events that may not result in death, are not life-threatening, or do not require hospitalization may be considered a SAE when, based upon appropriate medical judgment, they may jeopardize the subject's health or may require medical or surgical intervention to prevent one of the outcomes listed in this definition. For this study, examples of such events may include allergic bronchospasm requiring intensive treatment in an emergency room or at home, blood dyscrasias, or convulsions that do not result in subject hospitalization.

In addition, abortion (spontaneous or induced), fetal demise, and still birth along with congenital abnormalities in the newborn should be reported as separate SAEs (see Section 11.1.3).

Some hospitalization scenarios do not require reporting as an SAE if there is no occurrence of an AE. These scenarios include a planned hospitalization or prolonged hospitalization to:

- Perform a routine control screening for a preexisting illness or to diagnose a suspected illness. In the case of the latter, the symptomatology should be reported as an AE and amended if a diagnosis is confirmed.
- Undergo a diagnostic or elective surgical procedure for a preexisting medical condition that has not changed (eg, a joint replacement for which the subject was on a waiting list).
- Undergo medical observation due to HAE (eg, admission after routine dental procedure in a subject with HAE).
- Undergo medical observation without the occurrence of an AE due to standard of care in the region or hospital.

Overdose will be considered an SAE only if any of the seriousness criteria are met. Any clinical complication in association with the overdose should be reported as an AE or SAE (as applicable) along with the overdose (see Section 11.2.3). Details of signs or symptoms, clinical management, and outcome should be reported, if available. Overdose without associated signs or symptoms should not be recorded as AEs but should be recorded as protocol deviations.

11.1.1.3. Adverse Events of Special Interest

For this protocol, no events of special interest have been identified.

11.1.1.4. Definition of Severity

All AEs and SAEs will be assessed (graded) for severity by the investigator and classified using the Division of AIDS (DAIDS) table for grading the severity of adult and pediatric AEs (Publish date July 2017). Any AEs not covered by the DAIDS table will be assessed and classified into 1 of 5 clearly defined categories as follows:

- Mild:** (Grade 1): Mild symptoms causing no or minimal interference with usual social & functional activities with intervention not indicated.
- Moderate:** (Grade 2): Moderate symptoms causing greater than minimal interference with usual social & functional activities with intervention indicated.

Severe: (Grade 3): Severe symptoms causing inability to perform usual social & functional activities with intervention or hospitalization indicated.

Life-threatening: (Grade 4): Potentially life-threatening symptoms causing inability to perform basic self-care functions with intervention indicated to prevent permanent impairment, persistent disability, or death.

Death: (Grade 5): Indicates death related to the AE.

The investigator should report the highest severity experienced during the course of the event. It is important to distinguish between serious and severe AEs. Severity is a measure of intensity, defined above, whereas seriousness is defined by the criteria under Section 11.1.1.4. An AE of severe intensity may or may not be considered serious. An example would be a severe headache that does not result in any serious outcome is a non-serious AE; conversely, a mild event that results in hospitalization is a serious AE.

11.1.1.5. Definition of Relationship to Study Drug

Using the following guidelines, an investigator who is qualified in medicine must make the determination of relationship to berotralstat or SOC HAE medication used for prophylaxis and/or acute therapy for each AE (not related or related). The investigator should decide whether, in his or her medical judgment, there is a reasonable possibility that the event may have been caused by berotralstat or SOC HAE medication. If no valid reason exists for suggesting a relationship, then the AE should be classified as “not related.” If there is any valid reason, even if undetermined, for suspecting a possible cause-and-effect relationship between berotralstat or SOC HAE medication and the occurrence of the AE, then the AE should be considered “related.”

Because multiple study drugs are being administered in this study, the investigator should assess causality individually to berotralstat or SOC HAE medication, taking into consideration the timing of the AEs in relation to berotralstat or SOC HAE medication dosing as well as the known safety profile of berotralstat or SOC HAE medication.

The degree of certainty with which an AE is attributed to berotralstat or SOC HAE medication (or alternative causes, eg, natural history of the underlying disease, concomitant therapy) will be determined by how well the experience can be understood in terms of one or more of the following:

- Known pharmacology of berotralstat or SOC HAE medication
- Reactions of a similar nature have been previously observed with berotralstat or SOC HAE or these classes of drugs
- The experience being related by time to berotralstat or SOC HAE medication, terminating with their withdrawal or recurring on re-challenge
- Alternative cause

The investigator should assess causality by determining whether the AE/SAE is suspected to be caused by the investigational product based on facts, evidence, science-based rationales, and clinical judgement as follows:

- Not Related:** The temporal relationship of the AE/SAE to investigational product administration makes a causal relationship unlikely, OR other drugs, therapeutic interventions or underlying conditions provide a sufficient explanation for the AE/SAE.
- Related:** The temporal relationship of the AE/SAE to investigational product administration makes a causal relationship possible, AND other drugs, therapeutic interventions or underlying conditions do not provide sufficient explanation for the AE/SAE.

The sponsor may upgrade causality if deemed appropriate.

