11.3. Data Monitoring Committee

An independent DMC will be established for interim safety monitoring. The specific responsibilities and composition of the DMC are outlined in a separate DMC charter. The charter will include, at a minimum, a description of DMC membership, roles, timing of DMC review and responsibilities of DMC members. In addition, the details of outputs provided for the meetings will be referenced in this charter.

The DMC will be convened according to FDA guidelines. In general, the DMC will review safety data on an ongoing basis and SAEs considered related to berotralstat as they occur. Prior to initiating dosing with berotralstat (ie, initiation of Part 1) in Cohorts 3 and 4 (and any subsequent cohorts), the DMC will meet and review safety data and endorse opening of all subsequent cohorts.

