11.1. Adverse Events

AEs will be assessed and recorded from the time of signing of the informed consent through the last follow-up visit or until the AE is resolved or the subject is in a clinically stable condition with regards to the AE. AEs will be assigned as pre-treatment, treatment-emergent, or post-treatment according to the start date of the event. Events occurring prior to the start of study drug (ie, berotralstat) will be considered pretreatment and any AE reported as related to treatment will be attributed to SOC treatment and not berotralstat. Events starting on or after the initiation of study drug (ie, berotralstat) in Part 1 will be considered treatment-emergent or post-treatment and any AE reported as related to treatment during these periods will be assigned to berotralstat.

AEs will be mapped to system organ classification and PT using MedDRA version 25.0. Relationship to study drug will be assessed as not related or related. AEs will be graded according to the DAIDS table for grading the severity of adult and pediatric AEs (Publish date July 2017, see Protocol Appendix Section 15.1). AEs not covered by the DAIDS table will be assessed and classified into 1 of 5 severity categories: mild, moderate, severe, life-threatening, and death, corresponding to toxicity Grades 1 through 5. Should an event have a missing relationship or severity, these events will be classified as 'related' or 'severe'.

The duration of AEs in days will be derived and presented in all listings; this value is calculated as (AE stop date/time – AE start date/time). Both start and stop dates must be present to calculate a duration. Duration will not be calculated if either the start or stop date is imputed.

No events of special interest have been identified in this protocol.

TEAEs are defined as AEs that occurred on or after first dose of berotralstat through 30 days post discontinuation of study treatment. All AEs that occurred prior to the initiation of berotralstat or those recorded after 30 days after the last dose of berotralstat will be excluded from the tables but will be included in the listings. All AEs will be listed for individual subjects showing both verbatim and preferred terms.

An overall summary of AEs will be produced to summarize the number and percentage of subjects reporting:

- Any TEAE
- Any treatment-emergent SAE (TESAE)
- Any drug related TEAE
- Any drug related TESAE

- Any Grade 3 or Grade 4 TEAE

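### Protocol 11.1.1.5 holds two tests for a related adverse event, and they disagree when the drug is validly suspected but another cause would also suffice

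*Protocol*

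**What the plan says.** Protocol 11.1.1.5 asks the investigator for a two-way causality judgement and states the test twice.

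- **Opening test.** The event is related "If there is any valid reason, even if undetermined, for suspecting a possible cause-and-effect relationship between berotralstat or SOC HAE medication" and its occurrence. The counterpart is equally broad: "If no valid reason exists for suggesting a relationship, then the AE should be classified as" not related. Both berotralstat and standard-of-care (SOC) HAE medication are covered, and each is to be judged separately. A list of considerations follows, in which an alternative cause is one item bearing on the degree of certainty.
- **Closing definitions.** The event is not related on either of two grounds. One is timing: "The temporal relationship of the AE/SAE to investigational product administration makes a causal relationship unlikely". The second is a competing cause, which is enough by itself: "OR other drugs, therapeutic interventions or underlying conditions provide a sufficient explanation for the AE/SAE". It is related when timing makes a link possible, "AND other drugs, therapeutic interventions or underlying conditions do not provide sufficient explanation for the AE/SAE". These definitions refer only to the investigational product, which the protocol synopsis identifies as berotralstat.

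The section ends: "The sponsor may upgrade causality if deemed appropriate". No criteria are given.

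SAP 11.1 adds no definition: "Relationship to study drug will be assessed as not related or related". It attributes related events before the first berotralstat dose to SOC treatment and later ones to berotralstat. SAP 8.5.8 sets a missing relationship to related.

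**The concern.** The two tests have opposite defaults. Under the opening test a valid suspicion settles the matter in favour of related. Under the closing definitions a sufficient alternative settles it in favour of not related, whatever grounds remain for suspecting the drug. No sentence ranks one above the other, so two investigators can code the same event differently and both comply with the protocol.

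The answer feeds the drug-related TEAE, serious TEAE and Grade 3/4 tables (14.3.1.4, 14.3.1.6 and 14.3.1.8), the drug-related rows of the overall summary, and the related-event listings. It also feeds SUSAR classification (Protocol 11.1.3.3) and decides whether an SAE falls among the "SAEs considered related to berotralstat as they occur" that the DMC reviews (Protocol 11.3).

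The scope mismatch matters separately. SAP 11.1 tabulates drug-related AEs in the SOC period, and Protocol 4.4.4 makes that period a control for safety. Read literally, the closing definitions give no route to related before berotralstat has been given. The two periods could then be judged by different standards.

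**Working it through.** The plan gives no figure on causality to reproduce. Its one safety probability (Protocol 12.1, about 96%) is 1 − 0.9^30 = 0.958. It concerns any TEAE regardless of cause, so it is not involved here.

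**Step 1: compare the tests.** Let V = a valid reason to suspect the drug, T = timing makes a link possible, A = another cause is a sufficient explanation. The opening test gives related if V. The closing definitions give related if T and not A.

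| V | T | A | Opening test | Closing definitions | Agree? |
|---|---|---|---|---|---|
| yes | yes | yes | related | not related | **no** |
| yes | yes | no | related | related | yes |
| yes | no | yes | related | not related | no |
| yes | no | no | related | not related | no |
| no | yes | yes | not related | not related | yes |
| no | yes | no | not related | related | no |
| no | no | yes | not related | not related | yes |
| no | no | no | not related | not related | yes |

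The first row carries the point. The other three disagreements need odd combinations: a valid suspicion although timing makes a link unlikely, or no valid suspicion although timing fits and nothing else explains the event. Little weight should rest on those.

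**Step 2: is the first row realistic?** Protocol 4.4.5 names abdominal pain, vomiting, diarrhea and reflux as reactions seen at 150 mg once daily. On-demand HAE medication continues throughout the study. Vomiting or diarrhea on berotralstat, with an infection suspected but not diagnosed or soon after an on-demand drug, fits the row if the investigator judges that other cause sufficient.

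**Step 3: size.** The documents do not allow a count of such events. What can be computed is the weight of one subject whose only drug-related TEAE is of this kind. The change in the drug-related percentage is 100 × 1/n.

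- All cohorts, n = 30 (planned enrollment, assuming all are treated): 100/30 = 3.3 points.
- A cohort of 4 (minimum for Cohorts 1 to 3): 100/4 = 25 points.
- A cohort of 3 (minimum for Cohort 4): 100/3 = 33.3 points.

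**Step 4: can anything downstream repair it?** The SAP default for a missing relationship acts on blanks only. The sponsor's upgrade is optional and runs in one direction, and the SAP does not say whether the tables use the investigator's value or the upgraded one.

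**The case against.** The best counter-argument is that the section contains one test. It asks for a medical judgement of reasonable possibility, lists alternative cause among the considerations, and ends with definitions that put the judgement into practice. An investigator could hold that a sufficient alternative removes the valid reason. This shows how a site might reconcile the wording, but it does not make the wording consistent. A known reaction with compatible timing remains a reason to suspect the drug even when something else would also explain it, and the opening test reserves not related for events with no such reason. CRF completion guidelines, which are not among the documents, may settle practice; the protocol does not.

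Several stronger readings are tempting and should be resisted.

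- A reader might infer that any plausible alternative changes the class. The closing definitions require a sufficient one.
- A reader might take abdominal symptoms of HAE, or vomiting in a diagnosed viral illness, as examples. HAE attack symptoms are not AEs (Protocol 11.1.1.1), and a diagnosis replaces its symptoms as the recorded event (Protocol 11.1.2).
- A reader might infer that an SAE coded not related escapes the DMC. It loses only review as it occurs. The DMC also reviews safety data on an ongoing basis, and every SAE must be reported within 24 hours whatever its causality (Protocol 11.1.3.1).
- A reader might want to say what share of related events is lost. Nothing in the documents supports a figure.

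**Conclusion.** The contradiction is real and worth correcting, but its reach is limited. It bites when suspicion of the drug is valid, timing is compatible and another cause is sufficient. The closing definitions then give fewer related events than the opening test. How many fewer is unknown. The per-subject shifts of 3.3, 25 and 33 points assume 30 treated subjects or cohorts at their minimum size, and a subject with no other drug-related TEAE.

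The drug-related summaries and listings, SUSAR classification and as-they-occur DMC review are affected. All-causality tables, ongoing DMC review and 24-hour SAE reporting are not. No inferential testing is planned, so no hypothesis test is at risk. The narrower scope of the closing definitions is a second, separate inconsistency, and it affects the SOC-period summary of drug-related AEs.

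**What to change.** 1. Use one definition in Protocol 11.1.1.5. Keep the reasonable-possibility test, under which any valid reason for suspicion is enough, and remove the clauses that let an alternative explanation decide alone. This fits the section's own list, where alternative cause is one consideration among several.
2. Apply that definition to both berotralstat and SOC HAE medication.
3. Treat alternative cause as a factor. It may be recorded as a separate CRF item, but it should not override relatedness.
4. State in SAP 11.1 whether the tables use the investigator's causality or the value after any sponsor upgrade.
5. If events already recorded are re-reviewed, re-assess all of them under the single definition, in both directions. Querying only those coded not related could only raise the count.

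The cost is a wording amendment with IRB/IEC submission (Protocol 13.3.1) and updated CRF guidance. The drug-related rate may rise slightly.

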11.1.2. Recording Adverse Events

Information about AEs and SAEs will be collected from the signing of the ICF until the end of the study and will be recorded during the study at the investigational site in the CRF according to the instructions provided in the CRF completion guidelines.

The AE term should be recorded using standard medical terminology (not lay language). The investigator should attempt, if possible, to establish a diagnosis based on the presenting signs and symptoms. In such cases, the diagnosis should be documented as the AE and not the individual signs/symptoms. If a clear diagnosis cannot be established, each sign and symptom must be recorded individually. Once a diagnosis is made during evaluation or treatment, the investigator will update the AE record by replacing the individual signs and symptoms with this diagnosis.

11.1.2.1. Time Period for Follow-up of Adverse Events

All AEs that are ongoing at the time of the last study follow-up visit must be followed until they are resolved, or the subject is in a clinically stable condition with regard to the AE.

11.1.3. Reporting Serious Adverse Events and Suspected Unexpected Serious Adverse Reactions

11.1.3.1. Initial and Follow-up Reports

The investigator must report all SAEs immediately and in no case later than within 24 hours of their knowledge of the event. Investigators should adhere to their country or region requirements for the reporting timeframe which may not allow any delay. The initial and follow-up SAE reports will identify subjects by the unique subject numbers assigned to ensure that the sponsor will have the necessary information to continuously assess the benefit-risk profile of the study drug in the clinical study.

SAEs should be reported to the medical monitor and via the AE and SAE electronic CRFs (eCRFs). The SAE eCRF is an additional form to the AE eCRF that provides important details on the SAE. All additional follow-up evaluations of the SAE must be reported to BioCryst or its designee as soon as they are available. A notification of the SAE should be sent to the following email addresses:

Email: [contact]

In the event the eCRF system is not functioning, the reporting of an SAE must not be delayed. Sites will have SAE report forms (electronic Word document) that can be completed and emailed to the above recipients. As soon as the eCRF system is functioning, that particular SAE must be entered into the AE eCRF.

11.1.3.2. Pregnancy

Any female subject who becomes pregnant during the course of the study must have study drug/IMP discontinued immediately and must be followed through the end of the pregnancy. While pregnancy is not considered an AE, all cases of fetal drug exposure via the parent as a study participant (including partners of study participants) are to be reported immediately to BioCryst or its designee.

The Pregnancy Notification Form and Pregnancy Outcome Form should be sent to the following email address:

Email: [contact]

Consent from partners of study participants who become pregnant will be obtained prior to reporting any details of the pregnancy. Information related to the pregnancy must be given on a “Pregnancy Notification Form” and “Pregnancy Outcome Form” that will be provided by BioCryst so that the pregnancy may be followed, and an outcome determined. Any AEs or SAEs experienced by a pregnant subject are to be reported as directed in Section 11.1.2 and Section 11.1.3. Any complications reported in a subject’s pregnant partner should be reported on the “Pregnancy Notification Form” and “Pregnancy Outcome Form”. All pregnancies must be followed to outcome, which occurs when an infant is delivered (live or still born), there is fetal demise, or there is an abortion (spontaneous or induced). Abortion (spontaneous or induced), fetal demise, and still birth, along with congenital abnormalities in the newborn, should be reported as separate SAEs. The outcome of all pregnancies (spontaneous miscarriage, elective termination, normal birth, or congenital abnormality) must be followed up and documented, even if the subject was discontinued from the study.

11.1.3.3. Record Retention and Reporting to Regulatory Authorities

Investigators or designees at each site are responsible for retaining copies of all suspected unexpected serious adverse reaction (SUSAR) reports (initial and follow-up) and other safety information (eg, revised IB or Summary of Product Characteristics [SmPC]) in their investigator site files.

BioCryst or its designee will submit all SUSAR reports (initial and follow-up) or other safety information (eg, revised IB) to the required authorities, in accordance with the locally applicable regulations.

BioCryst or its designee shall ensure that all relevant information about SUSARs that are fatal or life-threatening is recorded and reported as soon as possible to all relevant competent authorities, and to the independent ethics committee (IEC)/institutional review board (IRB) in any case no later than 7 calendar days after knowledge by BioCryst of such a case, and that relevant follow-up information is subsequently communicated within an additional 8 days. All other SUSARs shall be reported to the competent authorities concerned and to the IEC/IRBs, as applicable according to local regulations, as soon as possible but in no case later than 15 calendar days of first knowledge by BioCryst. BioCryst or its designee shall also inform all investigators in accordance with local regulations. The investigator is responsible for ensuring that the IEC/IRB is also informed of the event, in accordance with local regulations.

